Patients eligible for this study will have advanced or metastatic urothelial carcinoma. Initial cohorts will enroll patients with documented disease progression on or after checkpoint inhibitor therapy. In the event results in the initial cohorts are of high interest for efficacy, patients naïve to checkpoint inhibitor therapy may be enrolled in additional study cohorts described in the protocol.

**Number in
Trial:**

Initial patient cohorts (Cohorts 1 and 2): as many as 80 patients.

Patient cohorts to be implemented in the event of high interest for efficacy:

- Contingent cohorts implemented and active as of this protocol version 4.0 (Cohorts 3 through 9): as many as 345 patients.
- Contingent cohort not yet implemented as of this protocol version 4.0 (Cohort 10): as many as 49 patients.

Primary Objective:

To evaluate the clinical activity of sitravatinib in combination with PD-(L)1 checkpoint inhibitor regimens in patients with advanced or metastatic urothelial carcinoma.

Secondary Objectives:

- To evaluate the safety and tolerability of the combination regimens in the selected population.
- To evaluate secondary efficacy endpoints of the combination regimens in the selected population.
- To evaluate the pharmacokinetics (PK) of sitravatinib administered in combination regimens.
- To evaluate the PK of sitravatinib in patients with renal impairment, to be implemented in selected study sites contingent upon early results in the study or sitravatinib program.
- Cohort 9 only: To identify recommended Phase 2 combinatorial doses (RP2Ds) of sitravatinib, pembrolizumab and enfortumab combination treatment.

Exploratory Objectives:

- To assess the effect of the combination regimens on circulating PD-L1, immune cell populations and cytokines.
- To assess the effect of the combination regimens on tumor cell PD-L1 expression, tumor infiltrating immune cell populations and gene expression signatures.
- To assess the correlation of tumor PD-L1 protein expression and gene alterations in circulation and in tumor tissue with treatment outcome.

Primary Endpoints:

Objective Response Rate (ORR) as defined by Response Evaluation Criteria in Solid Tumors version 1.1 (RECIST 1.1).

Secondary Endpoints:

- Safety characterized by type, incidence, severity, timing, seriousness and relationship to study treatment of adverse events and laboratory abnormalities.
- Secondary efficacy endpoints:
 - Duration of Response (DOR);
 - Clinical Benefit Rate (CBR);

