APPENDIX 4. ABBREVIATED PRESENTATION OF RECIST VERSION 1.1 GUIDELINES

A modification to RECIST 1.1 has been made to account for the possibility of temporary changes resulting from the potentially beneficial treatment responses of tumor necrosis, cavitation or flare response.

Categorizing Lesions at Baseline

Measurable Lesions

- Accurately measured in at least one dimension.
- When assessed by CT or MRI, longest diameter at least 10 mm or greater (slice thickness 5-8 mm), measured in the axial plane. If the slice thickness is greater than 5 mm (including any inter-slice gap), the longest diameter must be at least twice the slice thickness.
- Malignant lymph nodes with a short axis (defined as the largest measurement perpendicular to the longest diameter of the lesion) 15 mm or greater when assessed by CT or MRI.

The shortest axis is used as the diameter for malignant lymph nodes, longest axis for all other lesions.

Non-Measurable Disease

- Lesions too small to be considered measurable (including nodes with short axis between 10 and 14.9 mm) or truly non-measurable disease such as pleural or pericardial effusions, ascites, inflammatory breast disease, leptomeningeal disease, lymphangitic involvement of skin or lung, and abdominal masses identified by physical exam that are not measurable by reproducible imaging techniques.
- Bone disease is non-measurable with the exception of soft tissue components that can be evaluated by CT or MRI and meet the definition of measurability at baseline.
- Previously irradiated lesions (or those subjected to other local treatment) are non-measurable unless they have progressed since completion of treatment.

Normal Lesions

- Non-malignant simple cysts should not be recorded either as target or non-target disease. Cystic lesions thought to represent cystic metastases can be measurable lesions, if they meet the specific definition above.

- Lymph nodes with short axis <10 mm are considered normal and should not be followed as disease.

Tumor Assessments

All sites of disease must be assessed at baseline. Baseline assessments should be done as close as possible prior to study start. All required scans must be done within the window of time specified in the Schedule of Assessments prior to treatment. If the baseline assessment is inadequate, subsequent statuses generally should be indeterminate.

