Potential exists for individual tumor lesions to develop necrosis, to cavitate, have a flare response to treatment or become otherwise difficult to evaluate for a period of time as the result of beneficial study treatment impact. For example, tumor necrosis, cavitation or flare may result in increase in overall size of individual lesions or unclear tumor margins prior to recovery to smaller lesions, development of scar tissue, or complete resolution. The true tumor measurements of lesions should be recorded but the conclusion of progressive disease may be suspended until continued assessment clarifies the nature of the tumor change. If repeat assessments indicate progression of disease, then PD should be recorded on the date of the first assessment giving the impression of progression. If repeat assessments indicate that the change was a process of transition, then NE (not evaluable) should be recorded during the period of transition, and PR or CR may be recorded for subsequent evaluations. The CRF will collect information on the observations during the period of transition to support the assessment conclusions.

Supplemental Investigations

If CR determination depends on a residual lesion that decreased in size but did not disappear completely, it is recommended the residual lesion be investigated with biopsy or fine needle aspirate. If no disease is identified, objective status is CR.

Best Objective Response

Target Lesions	Non-Target Lesions	New Lesion	Point in Time Response	Best Response
CR	CR	No	CR	CR and PR require confirmation at least 4 weeks after first observation
CR	Non-CR/Non-PD	No	PR	
PR	Non-PD	No	PR	
SD	Non-PD	No	SD	SD requires an on-study assessment after at least 6 weeks on study. Unconfirmed PR or CR are reported as SD.
PD	Any	Yes or No	PD	
Any	PD	Yes or No	PD	
Any	Any	Yes	PD	

Subjective Progression

Patients requiring discontinuation of treatment due to worsening health status attributable to advancement of the malignancy under study but without objective evidence of disease progression should not be reported as PD on tumor assessment CRFs. This should be indicated on the end of treatment CRF as off treatment due to Global Deterioration of Health Status.

APPENDIX 5. CONTINGENT STUDY COHORTS IN PATIENTS PREVIOUSLY RECEIVING TREATMENT WITH SELECTED IMMUNOTHERAPIES

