11.6.5 Progression-Free Survival (PFS)

Progression-free survival (PFS) is defined as the time from the first dose of study drug to the date of PD or death due to any cause, whichever occurs first in the absence of documented PD. PFS (in months) will be calculated as $(\text{first event date} - \text{first dose date} + 1)/30.4375$.

PFS will be summarized descriptively using the Kaplan-Meier estimate. The median, 25th percentile, and 75th percentile of PFS and their two-sided 95% CI (Brookmeyer & Crowley, 1982) will be calculated where appropriate. In addition, minimum and maximum will also be displayed. Kaplan-Meier plots will be provided for PFS.

Analysis will be performed on the FAS.

Censoring Rules for DoR and PFS

The following censoring rules will apply to event dates for time-to-event endpoints that are based on radiographic evaluations, i.e., DOR and PFS:

- Endpoints will be censored on the date of first dose (or randomization) with duration of 1 day under the following scenarios, unless patients die within 2 consecutive tumor assessments of first dose (on or prior to week 16, i.e. Cycle 5 Day 1 plus the 10 day window, which is Study Day 122 for Cohorts 1-8 or Day 136 for Cohort 9), in which case they will be assessed as having an event on the date of death (apply to PFS only):
 - baseline disease assessment inadequate to apply RECIST1.1;
 - no disease assessments are performed during study treatment; or
 - all disease assessments performed during study treatment result in the conclusion of NE.
- Endpoints will be censored on the date of the last evaluable disease assessment prior to the start of subsequent anti-cancer therapy under the following scenarios (apply to PFS and DOR). Last evaluable assessment date is defined as the last response assessment date on or after treatment start date with a response of CR, PR, or SD.
 - PD or death occur after ≥ 2 consecutive tumor assessments (i.e., ≥ 122 days of last evaluable tumor assessment for Cohorts 1-8 or ≥ 136 days for Cohort 9) that are missed or result in the conclusion of NE;
 - patient administered subsequent anti-cancer treatment prior to documented PD or death;
 - patient lost to follow-up;
 - patient withdrawal of consent for follow-up; or
 - patients alive and without PD at the time of analysis

Date of death will be considered an event for DOR and PFS only if death occurred in the absence of receiving subsequent anti-cancer therapy, and under one of the following scenarios:

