Potential exists for individual tumor lesions to develop necrosis, to cavitate, have a flare response to treatment or become otherwise difficult to evaluate for a period of time as the result of beneficial study treatment impact. For example, tumor necrosis, cavitation or flare may result in increase in overall size of individual lesions or unclear tumor margins prior to recovery to smaller lesions, development of scar tissue, or complete resolution. The true tumor measurements of lesions should be recorded but the conclusion of progressive disease may be suspended until continued assessment clarifies the nature of the tumor change. If repeat assessments indicate progression of disease, then PD should be recorded on the date of the first assessment giving the impression of progression. If repeat assessments indicate that the change was a process of transition, then NE (not evaluable) should be recorded during the period of transition, and PR or CR may be recorded for subsequent evaluations. The CRF will collect information on the observations during the period of transition to support the assessment conclusions.

Supplemental Investigations

If CR determination depends on a residual lesion that decreased in size but did not disappear completely, it is recommended the residual lesion be investigated with biopsy or fine needle aspirate. If no disease is identified, objective status is CR.

Best Objective Response

Target Lesions	Non-Target Lesions	New Lesion	Point in Time Response	Best Response
CR	CR	No	CR	CR and PR require confirmation at least 4 weeks after first observation
CR	Non-CR/Non-PD	No	PR	
PR	Non-PD	No	PR	
SD	Non-PD	No	SD	SD requires an on-study assessment after at least 6 weeks on study. Unconfirmed PR or CR are reported as SD.
PD	Any	Yes or No	PD	
Any	PD	Yes or No	PD	
Any	Any	Yes	PD	

Subjective Progression

Patients requiring discontinuation of treatment due to worsening health status attributable to advancement of the malignancy under study but without objective evidence of disease progression should not be reported as PD on tumor assessment CRFs. This should be indicated on the end of treatment CRF as off treatment due to Global Deterioration of Health Status.

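### The criteria behind the RECIST 1.1 response rate let a measured progression be suspended and a later response counted, with no unmodified analysis planned and no default when no repeat scan follows

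*Protocol*

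**What the plan says.** **Label.** The Study Summary defines the primary endpoint as "Objective Response Rate (ORR) as defined by Response Evaluation Criteria in Solid Tumors version 1.1 (RECIST 1.1". Protocol 2.2.1 and SAP 6.2.1 use the same label.

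**Criteria applied.** Protocol Appendix 4 opens: "A modification to RECIST 1.1 has been made to account for the possibility of temporary changes resulting from the potentially beneficial treatment responses". SAP Appendix 3 repeats it. For necrosis, cavitation, flare or lesions that are otherwise hard to evaluate, "the conclusion of progressive disease may be suspended until continued assessment clarifies the nature of the tumor change". No time limit is stated. Two outcomes follow:

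- The repeat scan shows progression: "If repeat assessments indicate progression of disease, then PD should be recorded on the date of the first assessment giving the impression of progression".
- The repeat scan shows a transition: "NE (not evaluable) should be recorded during the period of transition, and PR or CR may be recorded for subsequent evaluations".

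**Response rules.** SAP 11.6.1 counts no response after PD. Its Table 9 classes PR then PD as SD or PD, but accepts PR, NE, PR as a confirmed PR. The presented best responses are the investigator's. Central review is only a possibility, for Cohorts 7 through 10 (Protocol 7.1).

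**Censoring.** SAP 11.6.5 censors PFS and DOR at the last scan read as CR, PR or SD in several cases, including "patient administered subsequent anti-cancer treatment prior to documented PD or death", loss to follow-up and withdrawal of consent. If every scan is NE, PFS is censored at first dose.

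**The concern.** There are two separate issues.

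The first concerns ORR. Whether a scan is PD or NE decides whether later shrinkage may count. An investigator who knows the treatment makes that call, in an open-label study without randomization. The reported rate is then a modified-criteria rate under an unmodified label, and nothing planned tells the reader how many responses depend on the difference.

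The second concerns PFS and DOR. Both branches of the appendix presuppose a repeat assessment. A patient whose lesions have grown past the threshold and who moves to another therapy before a repeat scan fits neither. Such a patient is likely to be progressing, so censoring is informative and tends to lengthen estimated PFS and DOR.

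**Working it through.** **1. Effect on ORR.** Take PR at scan 1, a target-lesion increase meeting the PD threshold at scan 2, and PR at scan 3.

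- Scan 2 called PD: Table 9 gives SD or PD, and scan 3 cannot count. Non-responder.
- Scan 2 recoded NE after scan 3: PR, NE, PR is a confirmed PR. Responder.

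A response confirmed before scan 2 stands either way. A response that needs scan 3 stands only under NE. For scans meeting the threshold, the recode can therefore add a response but not remove one.

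**2. No repeat scan.** The documents do not say how the suspended scan is then coded. I read it as NE, since no PD has been recorded. Suppose new therapy starts next.

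- The suspended scan is the only post-baseline scan. Called PD: best response PD, PFS event at that scan. Suspended: best response NE, PFS censored at Day 1.
- An earlier scan was SD after at least 42 days. Best response is SD either way. Called PD: PFS event at the second scan. Suspended: PFS censored at the SD scan.
- The patient is already a confirmed responder. The response stands, and DOR is censored at the last CR, PR or SD scan instead of ending at the measured progression.

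The Table 9 row that gives PD with no further evaluation does not help, because it needs a time point already recorded as PD. Without a later scan there can be no later confirmed response, so this gap leaves confirmed ORR unchanged.

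**3. Reproducing the plan's figures.** For Cohorts 1–4 (Protocol 9.1): 9 patients, continue with at least 1 response, 17 in total, pass with at least 3.

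P(pass) = Σ over x₁ ≥ 1 of b(9, x₁, p) × P(X₂ ≥ 3 − x₁), with X₂ ~ Bin(8, p).

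At p = 0.05:
- P(X₁ = 0) = 0.95⁹ = 0.6302 (stated early termination 0.63).
- P(X₁ = 1) = 0.2985 and P(X₂ ≥ 2) = 0.0573; product 0.0171.
- P(X₁ = 2) = 0.0629 and P(X₂ ≥ 1) = 0.3366; product 0.0212.
- P(X₁ ≥ 3) = 0.0084.
- Sum, before rounding: 0.0466, as stated. At p = 0.30 the formula gives 0.9045, also as stated.

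For Cohorts 5–6 (Protocol Appendix 6: at least 6 of 24, then at least 14 of 45) the same method gives early termination 0.656, Type 1 error 0.0483 and power 0.9001, all agreeing with the plan.

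**4. Illustration.** Let d be the share of patients moved from measured PD to confirmed response. The documents give no value for d, so every value below is an assumption. If the rate without the modification equals the null rate, P(pass) is evaluated at p₀ + d:

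| d | 9/17 rule, p₀ = 5% | 24/45 rule, p₀ = 20% |
|---|---|---|
| 0 | 0.047 | 0.048 |
| 1 point | 0.073 | 0.068 |
| 2 points | 0.104 | 0.094 |
| 3 points | 0.140 | 0.125 |
| 5 points | 0.223 | 0.203 |

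**5. One patient.** In a 17-patient cohort, one recoded patient turns 2 responses into the 3 the rule asks for. At 40 patients, going from 5 to 6 responders moves the Clopper-Pearson lower limit from 4.2% to 5.7%, across the 5% null.

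**The case against.** The case against has real weight.

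- **Disclosure.** The modification is prespecified. Protocol 7.1 announces it, Protocol 9.4.1 and SAP 11.6.1 point to the appendices, and both appendices open with it. A reader might infer concealment; the documents do not support that. What stands is the unqualified label where the endpoint is defined.
- **The missing default and ORR.** A reader might infer that the missing default inflates the response rate. It cannot, as step 2 shows. ORR moves only through the branch where NE is followed by response.
- **Narrowness.** An unequivocal new lesion is still PD. A repeat scan showing progression is back-dated. NE followed by a single PR is only SD, and confirmation is still required. Lesions that cannot be measured accurately are already indeterminate under the ordinary target-lesion rules. All of this stands and suggests a small group, but does not empty it.
- **Continued follow-up.** Patients who stop for reasons other than objective progression keep being scanned until progression, new therapy or death. A death without new therapy within 122 days (Cohorts 1–8) or 136 days (Cohort 9) of first dose or of the last evaluable scan is still an event. So not every suspended progression without a repeat scan is lost. The exposed cases are mainly new therapy, withdrawal and loss to follow-up.
- **Benchmarks.** A reader might infer that the 5%, 10% and 20% reference rates assume unmodified RECIST 1.1. The plan simply assumes those rates and states no progression-handling rule for them, so the mismatch cannot be shown.
- **Data already planned.** True measurements, transition observations and response listings will exist. What is missing is the analysis that uses them.

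**Conclusion.** The point holds in two limited parts. First, the endpoint carries an unmodified label while the criteria allow a one-way recode for scans that meet the progression threshold, and no analysis shows its effect on ORR. Second, a suspended progression with no later evaluable scan has no default, which affects best response, PFS and DOR.

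The stated error rates are correct for their inputs and are not disputed. The size of any shift cannot be derived from the documents. The table in step 4 assumes d, and it treats a response after a measured progression as one that should not count, which is the unmodified convention and not a judgement on whether that response is genuine. Nor would one extra responder decide a cohort alone: 3 of 17 only means that further investigation may be warranted, and Protocol 9.1 bases expansion on more than ORR. This is an inexpensive improvement worth making, not a fault that invalidates the primary analysis.

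**What to change.** Amend SAP 11.6.1 and 11.6.5:

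1. **Default.** Analyse a suspended progression with no later evaluable scan before new therapy, death or withdrawal as PD on the date of the first suspicious scan. This matches the back-dating already used when a repeat scan shows progression.
2. **Sensitivity analysis.** Repeat ORR, DOR and PFS with PD at the first assessment that meets the Appendix 3 target-lesion threshold or has a recorded new-lesion or non-target progression, and count no response afterwards. Use the recorded measurements, the qualitative non-target status and the CRF transition observations. Report how many patients are reclassified.
3. **Label.** Name the endpoint ORR by RECIST 1.1 as modified in Appendix 3.

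The cost is SAP wording and one extra table. The primary ORR analysis stays as it is, and SAP 5.0 already foresees an amended version before database lock. The downsides are a sensitivity ORR that may be slightly lower, and an incomplete reconstruction of suspended non-target progression, because non-target lesions are followed without measurements.

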Table 15: Pembrolizumab and Enfortumab Dose Levels.....165

TABLE OF FIGURES

Figure 1: Study Schema24

LIST OF ABBREVIATIONS

ADC	Antibody-Drug Conjugate
AE	Adverse Event
ALT	Alanine Aminotransferase
APC	Antigen Presenting Cells
AST	Aspartate Aminotransferase
AUC	Area Under the Curve
BCRP	Breast Cancer Resistance Protein
C _{ave,ss}	Average Steady State Plasma Drug Concentration During Multiple-Dose Administration
CBR	Clinical Benefit Rate
CFR	Code of Federal Regulations
CI	Confidence Interval
CIT	Checkpoint Inhibitor Therapy
C _{max}	Maximum Plasma Concentration
CR	Complete Response
CRF	Case Report Form
CRO	Contract Research Organization
CT	Computed Tomography Scan
CTA	Clinical Trial Application
CTCAE	Common Terminology Criteria for Adverse Events
ctDNA	Circulating Tumor Deoxyribonucleic Acid
DDI	Drug-Drug Interaction
DLT	Dose-Limiting Toxicity
DOR	Duration of Response
EC	Ethics Committee
ECG	Electrocardiogram
ECOG	Eastern Cooperative Oncology Group
EIU	Exposure In-Utero
FDA	Food and Drug Administration
GCP	Good Clinical Practice
GFR	Glomerular Filtration Rate
HDPE	High-Density Polyethylene
hERG	human Ether-a-go-go Related Gene
HGF	Hepatocyte Growth Factor

LIST OF ABBREVIATIONS (CONTINUED)

hr	Hour
IC ₅₀	Half Maximal Inhibitory Concentration
ICD	Immunogenic Cell Death
ICF	Informed Consent Form
ICH	International Council for Harmonisation
IFN- γ	Interferon Gamma
IgG4	Immunoglobulin G4
IND	Investigational New Drug
INR	International Normalized Ration
irAE	Immune-related Adverse Event
IRB	Institutional Review Board
IUD	Intrauterine Device
kg	Kilogram
MAb	Monoclonal Antibody
MDSC	Myeloid-Derived Suppressor Cell
MDSCs	Myeloid-Derived Suppressor Cells
MedDRA	Medical Dictionary for Regulatory Activities
MET	Mesenchymal-Epithelial Transition
mg	Milligram
mITT	Modified Intent-to-Treat
mL	Milliliter
MMAE	Microtubule-inhibitor Monomethyl Auristatin E
MRI	Magnetic Resonance Imaging
mRNA	Messenger Ribonucleic Acid
MSCs	Mesenchymal Stem Cells
MTD	Maximum Tolerated Dose
MUGA	Multigated Acquisition Scan
NCI	National Cancer Institute
NE	Not Evaluable
NK	Natural Killer
NPCB	No Prior Clinical Benefit
NSCLC	Non-Small Cell Lung Cancer
ORR	Objective Response Rate

LIST OF ABBREVIATIONS (CONTINUED)

OS	Overall Survival
PCB	Prior Clinical Benefit
PD	Objective Progression of Disease
PD-1	Programmed Cell Death 1
PD-L1	Programmed Cell Death Ligand 1
PFS	Progression-Free Survival
P-gp	P-glycoprotein
PK	Pharmacokinetics
PKAP	Pharmacokinetic Analysis Plan
PPE	Palmar-plantar Erythrodysesthesia
PR	Partial Response
PTT	Partial Thromboplastin Time
Q2W	Every 2 Weeks
Q3W	Every 3 Weeks
Q4W	Every 4 Weeks
QD	Once Daily
QTc	Corrected QT Interval
RP2D	Recommended Phase 2 Combinatorial Dose
REB	Research Ethics Board
RECIST	Response Evaluation Criteria in Solid Tumors
RTKs	Receptor Tyrosine Kinases
SAE	Serious Adverse Event
SAP	Statistical Analysis Plan
SD	Stable Disease
SOC	System Organ Class
TAM	Tyro3, Axl and MERTK
TCR	T-Cell Receptor
TKIs	Tyrosine Kinase Inhibitors
TME	Tumor Microenvironment
Tregs	T Regulatory Cells
ULN	Upper Limit of Normal
WBC	White Blood Cell
WHO	World Health Organization

LIST OF ABBREVIATIONS (CONTINUED)

WOCBP	Women of Childbearing Potential
µg	Microgram
µM	Micromolar

